Phase 1 - The Use of Rhythmic Light Therapy to Entrain Gamma Oscillations and the Circadian System in Patients With Alzheimer's Disease

PI: [name]

NCT05015478

Document Date: 2-1-2024

A. Specific Aims

Data suggest that approximately 40% of the estimated 5.5 million older (65+) Americans with Alzheimer's disease (AD) suffer from severe dysfunction of sleep-wake and circadian systems, manifesting clinically as sundowning, excessive daytime sleepiness, nocturnal wandering, agitation, and day-night reversal, which substantially increases the burden of caregivers.^{1, 2} In people with mild cognitive impairment (MCI), an "at risk" or potential prodromal stage of dementia, sleep-wake disturbance is evident in up to 60% of patients.^{3, 4} It has also been shown that coherent 40 Hz neural oscillation is a fundamental frequency of healthy brain activity⁵ and it is believed to play a role in attentional selection and memory operations.⁶ ADRD patients in particular, have reduced gamma oscillations. Animal studies showed that exposing mice to flickering lights at 40 Hz reduces Aβ42 levels in cortical regions of the brain.

Our team has published various studies showing the positive impact of a tailored lighting intervention (TLI) designed to promote circadian entrainment in persons with ADRD. In addition, we recently collected and published on exciting pilot data showing that light modulating at 40 Hz increases gamma power and gamma/theta coupling, both associated with increase in memory and cognition. **In Aim 1, we will investigate how the light delivering 40 Hz to promote gamma wave entrainment (rhythmic light [RL]), affects subjective sleep and cognition in a controlled laboratory study. A lab study will allow us to collect electroencephalogram (EEG), perform cognitive tests, and observe the response in those with MCI compared to a healthy control group (HC).**

Aim 1: In a randomized, placebo-controlled, mixed-design laboratory study, we will demonstrate the effect of 40 Hz RL on: 1) brain response (EEG), 2) cognitive performance (working memory task), and 3) subjective sleepiness (questionnaires). We will recruit 20 adult MCI and 20 healthy, age-matched controls (HC) to participate in this study. It is hypothesized that compared to the placebo intervention (i.e., random flicker): 1) 40 Hz RL will increase gamma (40 Hz) neural oscillation and increase theta-gamma coupling, 2) improve cognitive performance and 3) reduce subjective sleepiness. We also hypothesize that gamma power will be reduced in MCI participants and the effect size of the intervention will be greater in MCI participants than in the HC.

We will, for the first time, demonstrate that a practical, effective, tailored, nonpharmacological intervention using light that promotes circadian entrainment (TLI) and deliver neurostimulation (40 Hz RL) can be used to improve sleep and cognition in older adults with MCI and mild AD living at home or in independent or assisted living facilities, thereby possibly mitigating significant financial and social burdens, including decreasing cognitive deterioration in this population. Moreover, given recent evidence linking the importance of sleep in the development of AD, the proposed studies can have a significant impact on the progression of the disease MCI and mild AD.

Aim 1: Participant Recruitment. Population/Sample: Community Persons Living with Mild Cognitive Impairment (MCI) or mild Alzheimer's disease (AD) and Healthy Age-matched Controls (HC).

a. Study sites: Participants will be recruited from the Capital District and NYC area in conjunction with physicians who have access to the clinical population. Our team have demonstrated the ability to recruit older adults, including those with AD and their caregivers, in 3 recent NIH-funded trials. As in prior successful trials, recruitment methods will include: (1) provider referral, (2) on-site (in assisted living) by research staff, (3) flyers placed in participating sites or through advertising in the community, and (4) social media. We plan to collect equal numbers of participants in winter and summer to account for a possible effect of season and equal number of males and females.

b. Procedures: [name] team, with referrals from local physicians already working with her, will enroll 40 participants (20 controls) for **Aim 1**. Participants must be diagnosed with amnestic MCI or mild AD, as defined by a Montreal Cognitive Assessment (MoCA)⁸⁷ score between 17 and 25. For the healthy controls, the inclusion criteria are: must not be diagnosed with MCI or ADRD (MOCA score above 25). All participants must not be taking sleeping medication or oral melatonin, those taking antidepressants will be included, but type of medicine and dosage intake will be monitored, must score a 5 or less in the Pittsburgh Sleep Quality Index (PSQI) and must not have any of the exclusion criteria below. Study participants who meet the inclusion and exclusion criteria will discuss informed consent for study participation, using procedures and consent forms approved by the Institutional Review Board.

Aim 1 - Screening Assessments

a. Cognitive screening utilizing the MoCA: The MoCA⁸⁷ is a one-page, 30-point test that can be administered in 10 minutes. It assesses short-term memory, visuospatial abilities, executive functions, attention, concentration and working memory, language, and orientation to time and place. In a validation study, it was shown to be a promising tool for detecting mild cognitive impairment and early AD onset compared to the MMSE. According to Nasreddine et al.,⁸⁷ the sensitivity and specificity of the MoCA for detecting MCI (n = 94 participants) were 90% and 87%, respectively, compared to 18% and 100%, respectively, for the MMSE. The sensitivity and specificity of the MoCA for detecting early AD (n = 93 participants) were 100% and 87%, respectively, compared to 78% and 100%, respectively, for the MMSE. MCI/mild AD participants must have a MOCA score between 17 and 25. The control group participants must have a MOCA of 25 or greater.

b. The Clinical Dementia Rating Scale Sum of Boxes (CDR-SOB): CDR will be obtained through semi-structured interviews of patients and informants, and cognitive functioning will be rated in 6 domains of functioning: memory, orientation, judgment and problem solving, community affairs, home and hobbies, and personal care. Each domain is rated on a 5-point scale of functioning as follows: 0, no impairment; 0.5, questionable impairment; 1, mild impairment; 2, moderate impairment; and 3, severe impairment (personal care is scored on a 4-point scale without a 0.5 rating available). The global CDR score will be computed using online algorithm (www.biostat.wustl.edu/~adrc/cdrpgm/index.html). The CDR-SOB score is obtained by summing each of the domain box scores, with scores ranging from 0 to 18. We will include those in boxes 0.5-4.0 (Questionable cognitive impairment to very mild dementia) and 4.5-9.0 (mild dementia). The CDR demonstrates good reliability^{88, 89} and has been validated against neuropathologic finding.⁹⁰⁻⁹²

c. Sleep disturbance using the PSQI: The PSQI is a tool that can be used to measure sleep quality in clinical populations, composed of 19 items that generate 7 component scores (subjective sleep quality, sleep latency, sleep duration, habitual sleep efficiency, sleep disturbances, use of sleep medication, and daytime dysfunction).⁹³ The sum of the 7 component scores yields a single global score. A global score >5 is considered to indicate sleep disturbances. For Aim 1, we will include those who have scores <5 (no sleep disturbances).

Aim 1 - Study Assessments

a. Electroencephalogram (EEG): EEG recordings will be taken 2 times per experimental session using a Bio-Semi ActiveTwo system (BioSemi, Amsterdam, NL). Prior to each session, electrodes will be applied to the participants' scalps according to the international 10–20 system.⁹⁴ Four electrodes will be placed along the midline of participants' crania at locations Fz (frontal), Cz (central), Pz (parietal), and Oz (occipital). Reference electrodes will be placed on the earlobes at locations A1 and A2. To record blinking, an electrode will be placed under each participant's right eye for electrooculographic (EOG) measurements. The power at 40 Hz, 4–8 Hz (theta), and 30–55 Hz (low gamma) frequency ranges will be calculated at each electrode site. Entrainment to the 40 Hz rhythmic stimulation will be assessed in terms of increases in power at 40 Hz. Theta-gamma coupling will be assessed using the modulation index (MI),⁹⁵ wherein each phase of theta (0–360° interval) was binned into eighteen 20° intervals. The standard Hilbert transform will be applied to obtain time series of theta phases and amplitude envelope of low gamma. The composite time series will then be constructed, which will yield the amplitude of low gamma oscillation at each phase of the theta rhythm. The mean amplitude of gamma at each theta bin will be calculated and normalized by dividing each bin value by the sum over the bins, resulting in the phase-amplitude distribution function. The gamma amplitude MI by theta phase will be calculated by measuring the divergence of the observed amplitude distribution from a uniform distribution.

b. Subjective Sleepiness. Participants will be asked to report a Karolinska Sleepiness Scale (KSS)⁹⁶ score 2 times per experimental session. The KSS outcome prompts participants to rate how sleepy or alert they are feeling on a scale ranging from 1 to 9, where 1 = "very alert," 3 = "rather alert," 5 = "neither alert nor sleepy," 7 = "sleepy, but no difficulty remaining awake," and 9 = "very sleepy, fighting sleep, an effort to remain awake."

c. Working Memory (WM) Task: This complex operation span task has been used to examine WM in MCI, AD,⁹⁷ and healthy older adults.⁹⁸ The WM task contains 9 practice (not included in final score) and 20 test trials. Participants view a serial visual display of letters and math problems. They are asked to hold the letters in memory while simultaneously determining if the simple math problems are correct (e.g., 7+5=13). The letter strings are 4-8 letters long + 4 repetitions of each. Each of the simple math equation is on the screen for 3000 ms and each letter is presented for 1000 ms. Participants are instructed to press the "M" key with their right hand if the simple math equation is correct and press the "V" key with their left hand if the equation is not correct. Math performance is measured in percent correct. Similar to Unsworth et al.,⁹⁹ we will only include data in the analysis if participants can performed equal and/or greater than 75% correct on the math equations. After each trial, a

question mark appears on the screen to signal the response period. Participants are asked to enter the letters in the same order they were presented. The recall part of the task will not be timed, and participants are not able to go to the next trial until the correct number of letters is entered. Then, a “Ready?” prompt appears on the screen and participants will press the space bar to start the next trial. Four breaks are inserted throughout the task. Participants are tested in the WM task before and after each experimental condition. Performance is assessed by calculating Accuracy and Reaction Time (RT).

d. Questionnaires to assess Fatigue, pain and depressive symptoms: Four questionnaires will be collected one time at the first session.

- The Fatigue Severity Scale (FSS) uses contains nine statements that rate the severity of fatigue symptoms on a rating from 1 to 7, which measures the severity of fatigue and its effect on a person's activities and lifestyle.
- Self-Description Inventory measures levels of self-evaluative behavior in terms of favorable and unfavorable personality attributes.
- The Beck Depression Inventory (BDI) is a 21-item, self-report rating inventory that measures characteristic attitudes and symptoms of depression.

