**Variables and Measures.** Rest-activity rhythms before and after the TLI and RL will be measured using **the actigraph (rest-activity) data**. The following measures will be calculated: (1) interdaily stability (IS), a ratio indicating the strength of coupling between the light-dark cycle and rest-activity rhythm over a 24-hour period; (2) intradaily variability (IV), an indication of the fragmentation of the rest-activity rhythm (i.e., the frequency of the transitions between rest and activity); (3) RA of the rest-activity rhythm, calculated as the difference between the means of the most active 10-hour period ( $M_{10}$ ) and the least active 5-hour period ( $L_5$ ) in the 24-hour pattern; and (4) measures of nighttime sleep (minutes of sleep, sleep onset latency, and sleep efficiency). Photopic light levels (lux) and CS values will be calculated from the light-dark data collected with the Daysimeter. Increases in IS and RA and a decrease in IV will be considered an improvement in rest-activity patterns. We will evaluate the change in these variables from baseline to the end of intervention period and the post intervention period to assess carryover effects. Questionnaires will allow us to evaluate QoL and sleep quality. For the **EEG data**, the power at 40 Hz, 4–8 Hz (theta), and 30–55 Hz (low gamma) frequency ranges will be calculated at each electrode position (i.e., Fz, Cz, Pz, and Oz). Entrainment to the 40 Hz rhythmic stimulation will be assessed in terms of increases in power at 40 Hz. Theta-gamma coupling will be assessed using the modulation index (MI).

**Sample Size and Estimated Statistical Power:** Studies for each aim will have enough power to detect the impact of the active intervention on the study measures. Based on our pilot study, a planned sample size of 20 in each group (including 30% attrition rate) will provide 95% power, using 2-sided alpha = 0.05 significance tests, to detect statistically significant differences in the means between 2 paired treatment conditions in Aim 1.

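### The modulation index takes its amplitude from a band that contains the 40 Hz response, and its raw value depends on recording length, so an MI change cannot be read as a coupling change; the direction of any bias is not determined.

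*Protocol*

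**What the plan says.** The Aim 1 hypothesis is that "40 Hz RL will increase gamma (40 Hz) neural oscillation and increase theta-gamma coupling", compared with random flicker. Both outcomes are defined in the protocol under Aim 1 – Study Assessments, a. Electroencephalogram.

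- Entrainment: "Entrainment to the 40 Hz rhythmic stimulation will be assessed in terms of increases in power at 40 Hz".
- Bands: "30–55 Hz (low gamma) frequency ranges will be calculated at each electrode site". The range includes 40 Hz.
- Coupling: "The standard Hilbert transform will be applied to obtain time series of theta phases and amplitude envelope of low gamma". Theta phase is "binned into eighteen 20° intervals", the mean low-gamma amplitude in each bin is "normalized by dividing each bin value by the sum over the bins, resulting in the phase-amplitude distribution function", and MI is obtained by "measuring the divergence of the observed amplitude distribution from a uniform distribution".

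The SAP (Variables and Measures) repeats the bands and names MI as the coupling measure. Its Statistical Analyses paragraph normalises every outcome at T2 to T1, giving a relative change that enters the mixed model. The protocol (Aim 1 – Experimental Protocol, b. Data collection) gives 3-minute EEG recordings and places T2 after the 1 h exposure. The text reviewed mentions no separate handling of 40 Hz in the MI, no chance correction, no rule on the amount of clean EEG, and no statement on whether the light is on during the T2 recording.

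**The concern.** The two EEG outcomes are presented as separate evidence, yet the signal that defines the first is part of the input to the second. MI describes the shape of the amplitude distribution over theta phase, not its level. Extra 40 Hz activity therefore alters MI whenever its theta-locking differs from that of the background, even if the background coupling has not changed. A change in MI, or its absence, could then be reported as a finding about coupling when it reflects 40 Hz power.

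There is a second, smaller problem. An estimated distribution over 18 bins is never exactly uniform, so raw MI is positive even with no coupling, and more so with less data. Artefact rejection can leave different amounts of clean EEG at T1 and T2, in the two conditions, or in the MCI and control groups. Taking T2 relative to T1 passes any such difference into the analysed variable.

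**Working it through.** **Inputs.** From the protocol: theta 4–8 Hz, low gamma 30–55 Hz, 18 bins, 3 min = 180 s. Assumed, because the documents do not give them: Kullback–Leibler divergence divided by ln 18, the sampling rate, the filters, the background modulation depth, and the strength and theta-locking of the 40 Hz response. The plan states no MI value or MI effect size, so there is no figure to reproduce. Its 95% power statement names no outcome and does not bear on this point.

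**Formula.** With p_j the normalised bin means, MI = (ln 18 + Σ p_j ln p_j) / ln 18. If p_j = (1 + m cos θ_j)/18 with small m, then MI ≈ m² / (4 ln 18). Overall level cancels; only the relative depth m remains. For m = 0.1: 0.01 / (4 × 2.890) = 8.7e-4. Simulated baselines are 5.8e-4 to 6.7e-4, the same order but lower; band-pass filtering, which this formula ignores, is the likely reason.

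**Added in-band activity.** Simulated 180 s recordings at 512 Hz, background depth 0.10, 16 runs per cell. Entries are MI divided by MI with nothing added. The last column removes 39–41 Hz before the envelope.

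| Added component | 0.1× power | 0.5× | 1× | 3× | 39–41 Hz removed |
|---|---|---|---|---|---|
| 40 Hz, no theta modulation | 0.87 | 0.44 | 0.23 | 0.05 | 1.03–1.12 |
| 40 Hz, depth 0.05 | 1.01 | 0.76 | 0.58 | 0.52 | 0.99–1.11 |
| 40 Hz, depth 0.10 (as background) | 1.07 | 1.25 | 1.26 | 1.20 | 0.98–1.11 |
| 40 Hz, depth 0.30 | 1.56 | 3.75 | 5.85 | 9.26 | 1.02–1.63 |
| All gamma scaled up | 1.02 | 1.02 | 1.07 | 0.99 | 0.99–1.07 |
| Broadband 30–55 Hz, no modulation | 0.93 | 0.48 | 0.29 | 0.10 | 0.09–0.94 |

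Background depth 0.30 gives the same pattern: at 1×, 0.17 with no modulation, 0.57 at half depth, 1.24 at equal depth, 3.10 at depth 0.60, and 0.25 for broadband.

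**A modest response, 0.25× background power (total gamma power × 1.25).** One run at 256 Hz, background depth 0.10, 40 replicates:
- no modulation: 5.9e-4 → 3.5e-4, ratio 0.59
- equal modulation: 5.9e-4 → 6.1e-4, ratio 1.03
- depth 0.30: 5.9e-4 → 1.45e-3, ratio 2.46

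A separate run gave 6.5e-4 → 4.2e-4 (0.65), 6.7e-4 (1.03) and 1.5e-3 (2.3). Over four runs the unmodulated ratio was 0.57 to 0.65.

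**What removing 40 Hz does.** In the 256 Hz run, with 39.5–40.5 Hz removed, the baseline was 5.2e-4. The unmodulated tone gave 5.2e-4, so that dilution is repaired. The depth-0.30 tone gave 5.4e-4, so its 2.46-fold rise almost vanishes. Broadband activity gave 3.7e-4 (3.7/5.2 = 0.71), so that dilution is not repaired.

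**Chance floor.** With zero coupling, raw MI averaged about 3.5e-5 at 180 s and 1.1e-4 at 60 s. This is close to inverse proportion to length: 3.5e-5 × 180/60 = 1.05e-4. Subtracting the mean of time-shifted surrogates left about 1e-5 or less. Suppose T1 has 180 s clean and T2 has 60 s (an assumption, since no clean lengths are given):
- no coupling: T2/T1 = 1.1e-4 / 3.5e-5 = 3.1
- baseline MI near 6.5e-4, floor treated as additive: (1.1e-4 − 3.5e-5) / 6.5e-4 = 12% apparent rise

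At the full 180 s the floor is 3.5e-5 / 6.5e-4 = 5% of that baseline.

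**The case against.** The strongest reply is that the plan may work as intended. The protocol's Specific Aims say that in the team's pilot gamma power and gamma/theta coupling rose together under 40 Hz light, which is not what simple dilution would suggest. T2 follows the exposure; if the light is off by then, a steady driven 40 Hz component may be small or absent. All recordings are nominally 3 minutes and every participant receives both conditions, so clean lengths may be similar. If the response to light is truly theta-modulated, whole-band MI is the index that captures it.

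Much of this stands. It rules out a claimed direction, and it rules out making the 40 Hz-removed index the main test: that index would discard a genuine theta-modulated 40 Hz gain, and if random flicker adds broadband activity it would repair one condition and not the other. It does not make MI separate from 40 Hz power. The pilot statement does not say how coupling was computed. If there is no 40 Hz rise at T2 the entrainment hypothesis fails; if there is one, the confounding is present. Nominal recording length is not clean length.

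A reader might go further and infer that a rise in 40 Hz power lowers MI and so biases the coupling hypothesis against the active light. That needs three things: a 40 Hz response less theta-locked than the background, a response still present in the T2 EEG, and less dilution under placebo. The documents establish none of them. A 40 Hz square wave with a 50% duty cycle does put 8/π² = 81% of its variance at 40 Hz, against an estimated 17–34% in 30–55 Hz for random flicker, depending on how its description is read. That makes unequal dilution plausible, but stimulus power is not brain response.

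**Conclusion.** The point holds in this form: as defined, MI is confounded with 40 Hz power, in a direction that the documents do not determine. It falls if the 40 Hz response follows theta less than the background does, is about unchanged if equally, and rises if more. At 0.25 times background power the simulated range runs from about 0.57 to about 2.5 times baseline with background coupling held fixed. Bias against the active light is one possibility within that range and is not shown. These ratios depend on assumed signal settings; only direction and rough size should be relied on, and the actual strength of the 40 Hz response at T2 is unknown.

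The chance floor is a separate and smaller effect: about 5% of a moderate MI at full length, but large where coupling is weak and clean lengths differ. Whether they will differ cannot be told from the documents. Both matters can be handled in the analysis and deserve correction before the data are analysed.

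**What to change.** Amend the EEG paragraph of the protocol and the Variables and Measures and Statistical Analyses paragraphs of the SAP.

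1. For each participant, compute MI on equal lengths of clean EEG at T1 and T2 and in both conditions.
2. Subtract from each recording's MI the mean MI of time-shifted surrogates from that recording. Analyse the corrected index as T2 − T1, because corrected values can be near zero or negative and a T2/T1 ratio would be unstable. This removes the chance floor; it does not remove the 40 Hz confounding, which item 3 addresses.
3. Keep whole-band (30–55 Hz) MI as the planned test. Prespecify as a sensitivity analysis MI with a narrow band around 40 Hz (for example 39.5–40.5 Hz) removed in both conditions and at both times, reported with 40 Hz and 30–55 Hz power. A whole-band change absent from the 40 Hz-removed index should not be described as a coupling change independent of the 40 Hz response.
4. State whether the light is on during the T2 EEG.

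The cost is a little analysis code, some SAP wording and the clean data trimmed to a common length. The 40 Hz-removed index loses any genuine theta-modulated 40 Hz activity, which is why it should accompany the planned index and not replace it.

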The flicker frequency of the 40 Hz RL used in Aim 1 will be 40 Hz and the stimulation will be a square wave with a 50 % duty cycle (i.e., 12.5 ms light- on and 12.5 ms light-off). In the Placebo RL condition, the duty cycle will be delivered with a random interval determined by a Poisson process with an average interval of 40 Hz. Both RL and Placebo RL conditions will provide a 30 lux of red light on a vertical plane at the eye level. The red light will be used because it does not affect the circadian system; therefore, we will be able to attribute observed effect to the flicker frequency utilized. We hypothesize that the improvement in cognition and subjective sleepiness will be greater in the 40 Hz RL compared to the random RL and the effect will be larger in persons with MCI.
